The investigational drug is a polyherbal Siddha formulation. It is proven as an anti-diabetic^{3, 4, 6}. Some studies have investigated the possible anti-diabetic properties of combination drug in animal models, one in a high fructose diet induced and another in alloxan diabetic rats^{3, 5}. The results of these studies show that the administration of the extracts reduced the blood sugar level. Gallic acid is the component present in the composition of investigational drug having anti-diabetic activity⁷. More over the same studies highlighted the anti-oxidant and anti-obesity effects of this drug. These effects are assumed to play a major role to reduce the chances of transition of IGT patients to established diabetics. According to ICMR-INDIAB study conducted

in 2011, 3.9 million are estimated to be in the state of prediabetes in Tamil Nadu. Projections for the whole of India would be 77.2 million pre-diabetic patients¹⁰. So a poly-herbal formulation which is more effective, cost effective and safety among prediabetes patients.

According to the above references life style modification is done holistically in this study with the study drug.

2. Clinical Study Objectives:

2.1 Primary objective:

To assess the efficacy of Siddha formulation in the individuals having Impaired Glucose Tolerance (IGT) – (Munneerizhivu). If, during treatment or after treatment OGTT 2 hours remain between 126 mg/dl and 140 mg/dl, fasting blood sugar between 70 mg/dl and 100 mg/dl and HbA1c is $\leq 6.0\%$ it will be treated as successful outcome of the treatment.

2.2 Secondary objective:

To determine the Toxicological data of Siddha formulation

[figure not shown]
3 Study Design:

Open labelled Randomized Controlled Clinical Trial.

There will be two arms in this study. To one group is assigned life style modification and test drug and to the other group Life Style Modification (LSM). Randomization will be achieved through Random numbers.

3.1 Allocation to treatment:

The subjects will be allocated to the drug interventional group and LSM group based on the Random numbers generated by the computer.

Schematic representation of Study Design

5 Criteria for Inclusion:

Subjects in their 3rd to 6th decade only will be included in this study. Subjects falling in any one of the following criteria i.e. 2 hours OGTT should be between 140 mg and 199 mg. Glycated hemoglobin (HbA1C) > 6.0% and <6.5% and Blood sugar – Fasting > 100 and =< 125 mg/dl will be included.

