7.2 Follow-up Procedure

A prospective observation will be done for a period of one month after completion of the trial (6 months) by both groups. The drug intervention will be withdrawn in the drug group and LSM group will be on normal life style to measure the efficacy of the trial drug and LSM in both the groups. A comparison (physical assessment and blood sugar (OGTT) between the trial and non-trial period will be drawn in the outcome.

8. Safety and Efficacy Assessments

Liver function test and renal function test are recorded before and after trial drug administration to measure the safety of the drug. OGTT, HbA1c and blood glucose levels also measured for efficacy of the drug. Lipid profile is tested to measure the complementary benefit of the drug in microvascular end arterial diseases.

9. Adverse Event Reporting

If any adverse drug reaction or adverse event is reported, the study subject will be referred to the Pharmacovigilance cell of the study centre. According to the advice of the Pharmacovigilance cell withdrawal or continuation of the study will be determined.

10. Statistical Methods/Data Analysis

All the data will be entered in the Microsoft excel and the data will be analyzed using SPSS Version 16. Quantitative data shall be given in mean and standard deviation. Prevalence

shall be given in proportion with 95% confidence interval. Association with risk factors shall be analyzed using chi square test and multivariate analysis. Correlation shall be analyzed using Karl Pearson, with significant level ($P < 0.005$ or $P < 0.05$). Comparison between means with Annovatest, difference between means assessed by paired t test. Further analysis will be extended depending upon the results at the end of the study.

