10.1 Study endpoints

10.1.1 Primary endpoint

During treatment or after treatment OGTT 2 hours result is < 140 mg/dl, fasting blood sugar is < 100 mg/dl and HbA1c is < 6.0 % it will be treated as successful outcome of the treatment.

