10.2 Sample size determination

60 is the sample size as per the phase (Exploratory trial) of the clinical trial. 30 subjects will be enrolled in each group.

11. Criteria for Success of Treatment

Prevention or non-transformation of IGT to full blown diabetes which is measured by the primary end point will be considered as criteria stated above.

12. Trial Monitoring and Data Analyses

The progress of the trial will be monitored by the Guide. Data analysis will be done by the investigator.

13. Ethical Review

Institutional Ethical Committee (IEC) of participating centre is sought for clearance certificate before the project is initiated. Patient's information sheet and informed consent form will be submitted (Regional Language - Tamil) along with project proposal for approval by IEC. Both will be maintained in duplicate. Consent form will be given to the subject and will be enrolled with proper consent. One copy of Patient Information Sheet (PIS) will be given to the patient at the time of entry to the trial.

Reference:

1. Shukla s.s et al fundamental aspects and basic concepts of Siddha medicines. SYST-Re pharm 2011; 2:48-54.
3. American Diabetes Association. Diagnosis and classification of diabetes mellitus. *Diabetes Care*.2010; 33:S62–S69.
4. Unwin N et al, Impaired glucose tolerance and impaired fasting glycaemia: the current status on definition and intervention. *Diabet Med*. 2002; 19:708–723.
5. International Expert Committee. International Expert Committee report on the role of the A1C assay in the diagnosis of diabetes. *Diabetes Care*. 2009; 32:1327–1334.
6. Anjana RM et al, Prevalence of diabetes and prediabetes (impaired fasting glucose and/or impaired glucose tolerance) in urban and rural India: Phase I results of the Indian Council of medical research-India Diabetes (ICMR-INDIAB) study, 2011, *Diabetologia*, 54:3022-7.
7. Diagnosis, Prognosis, and Treatment of Impaired Glucose Tolerance and Impaired Fasting Glucose, McMaster University Evidence-based Practice Center, Hamilton, Ontario, Canada
<http://archive.ahrq.gov/downloads/pub/evidence/pdf/impglucose/impglucose.pdf>

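### Section 10 lets the analysis grow according to the results, without separating added tests from planned ones and without fixing a between-arm test or a single significance level for the primary endpoint

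*Protocol*

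**What the plan says.** All references are to the protocol.

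- **Section 10, last sentence:** "Further analysis will be extended depending upon the results at the end of the study". No limit on number or type is given, and there is no statement of what such an analysis may support.
- **Section 10, planned methods:** "Association with risk factors shall be analyzed using chi square test and multivariate analysis" and "Comparison between means with Annovatest, difference between means assessed by paired t test". Neither sentence names an endpoint or a comparison between the two arms.
- **Section 10, significance level:** "Correlation shall be analyzed using Karl Pearson, with significant level ($P < 0.005$ or $P < 0.05" (closing bracket follows). This is the only level given. It is a choice of two, it sits in the correlation sentence, and sidedness is not stated.
- **Section 10.1.1:** the primary endpoint is a composite: "During treatment or after treatment OGTT 2 hours result is < 140 mg/dl, fasting blood sugar is < 100 mg/dl and HbA1c is < 6.0" per cent.
- **Section 8:** "OGTT, HbA1c and blood glucose levels also measured for efficacy of the drug", with no order among the three.
- **Section 11:** success of treatment is described as non-progression to diabetes, as measured by the primary endpoint.
- **Section 10.2:** 30 subjects per arm, 60 in all, justified by the trial being exploratory.
- **Sections 3 and 12:** "Open labelled Randomized Controlled Clinical Trial" and "Data analysis will be done by the investigator".

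**The concern.** A p-value has its stated error rate only if the test was chosen without reference to the result. Section 10 says the opposite for an open-ended set of further analyses: the results decide what is tested next. The person deciding is the investigator, who under Section 6.2.1 also acts as sponsor and supplies the drug.

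This would matter little if the planned efficacy test were pinned down, because added tests would then stand visibly apart from it. It is not. The chi-square test is assigned to risk factors, the paired t test compares a subject with himself or herself, and the analysis of variance is not linked to a measure or to the arms. With no fixed test and no single level, a reader of the final report could not tell from the protocol which p-value was the planned one. A favourable added test, for example in a subgroup defined by one of the factors collected on Form I A, could appear beside the planned analyses as evidence that the formulation works.

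**Working it through.** **Inputs.** From the protocol: 30 per arm (10.2) and per-test level 0.05 or 0.005 (10). Assumed, because the protocol gives no figure: no drug effect, two-sided tests, and one added two-level subgroup split on the same measure as the planned test. The protocol states no error rate for the extended analysis, so there is no figure of its own to reproduce. The reference is the nominal level of one fixed test, 5% or 0.5%.

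**Step 1, structure.** Let Z1 and Z2 be the between-arm test statistics in the two subgroups. Under no effect they are independent standard normal. If the first subgroup holds a fraction f of subjects, the overall statistic is approximately

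Z = √f · Z1 + √(1−f) · Z2.

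**Step 2, bounds.** The chance that at least one of the three tests is significant lies between the rate for the two subgroup tests alone and the rate if all three were independent.

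- At 0.05: 1 − 0.95² = 0.0975 and 1 − 0.95³ = 0.1426.
- At 0.005: 1 − 0.995² = 0.0100 and 1 − 0.995³ = 0.0149.

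**Step 3, exact value under the normal model.** With critical value c, integrate the joint density of Z1 and Z2 over the region where |Z1|, |Z2| and |Z| are all below c, and subtract from 1.

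| Per-test level | c | f = 0.5 | f = 0.7 |
|---|---|---|---|
| 0.05 | 1.960 | 0.115 | 0.114 |
| 0.005 | 2.807 | 0.0130 | 0.0127 |

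**Step 4, check at the trial's size.** Simulating 400,000 null trials of 30 per arm with t tests gave the following.

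| Per-test level | Single planned test | 15/15 split per arm | 20/10 split per arm |
|---|---|---|---|
| 0.05 | 0.050 | 0.116 | 0.114 |
| 0.005 | 0.005 | 0.0132 | 0.0129 |

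So one split raises the rate from 5% to 11–12%, or from 0.5% to about 1.3%. The ratios are 0.115/0.05 = 2.3 and 0.013/0.005 = 2.6.

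**Step 5, direction.** These rates count false positives either way. In the drug's favour only, the same integral gives 5.8% against 2.5% at the 0.05 level, again a ratio of 2.3.

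**Step 6, range over the unknown number of tests.** At 0.05 per test, one planned plus five added tests gives 1 − 0.95⁶ = 0.265 if independent, and 0.241, 0.207 and 0.163 at common correlations of 0.3, 0.5 and 0.7. At 0.005 per test, even 20 independent tests in total give 1 − 0.995²⁰ = 0.095, and ten give 0.049.

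**The case against.** **The sentence adds, it does not replace.** It speaks of extending the analysis. A reader might infer that a failed primary endpoint may be swapped for a favourable test. The protocol does not support that: Sections 10.1.1 and 10.1.2 name a primary and a secondary endpoint, and Section 11 measures success by the primary one. Swapping would depart from Section 11. This stands. What remains is that Section 11 is loosely worded, the success limits in Section 2.1 differ from those in 10.1.1, and no test is attached to the endpoint, so the restraint is weak.

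**Post hoc labels and multiplicity rules are usually SAP matters.** True, and their absence alone would be no finding. The fault lies in what is written: a results-driven rule, beside two alternative levels. An SAP could list planned tests and the sentence would still stand.

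**The trial is exploratory.** Section 10.2 says so, and follow-up analyses are ordinary in such a trial. This lowers the weight of the point. It does not remove it, because the word is used to justify the sample size and Section 2.1 sets the objective as assessing efficacy.

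**Larger figures are tempting.** Taking the best of OGTT, fasting glucose and HbA1c at 0.05 gives 12.6% at correlation 0.5 (9.8% at 0.8, 14.2% at 0), and adding a subgroup split gives 18.3%. A reader might charge these to the quoted sentence. But Section 8 already lists the three measures for efficacy, so testing each needs no further analysis. That is multiplicity among planned measures, a different question.

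**Open label adds little here.** Also fair: the extension is decided at the end of the study, when allocation is normally known even in blinded trials.

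**Conclusion.** The point holds in limited form. Section 10 states a results-driven rule for further analysis, does not separate its products from planned tests, and leaves the primary endpoint without a between-arm test or a single level. The protocol permits, but does not state an intention, that a test chosen this way be reported as evidence of efficacy. Running extra analyses is harmless; claiming efficacy from them unlabelled is what loses the error rate.

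The direction is certain and the size is not. With one added subgroup split the false-positive rate is 11–12% at 0.05 per test, or about 1.3% at 0.005, where a single fixed test would give 5% or 0.5%. Those figures rest on the assumed split, a measure analysed as approximately normal, and no drug effect. Exact tests on a yes/no endpoint in small subgroups are conservative and would run lower. If the stricter level were the one applied, the absolute rate would stay below 5% for this scenario. The change is worth making because it is nearly free and decides what the trial may conclude.

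**What to change.** Replace the last sentence of Section 10 with:

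> The efficacy conclusion rests only on the between-arm comparison of the proportion meeting the primary endpoint (10.1.1), by chi-square or Fisher exact test at two-sided 0.05, with a 95% confidence interval for the difference. Separate analyses of OGTT, fasting glucose and HbA1c are supportive. Any analysis added after results are seen is labelled post hoc, reported as an estimate with 95% confidence interval, and not used to claim efficacy.

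Two details go with it. The choice between chi-square and Fisher should be settled before analysis, for instance by a rule on expected cell counts. The success limits in 2.1 and 10.1.1 should be reconciled so that the sentence points to one definition. The false-positive rate of the efficacy claim is then held at about 5% however many analyses are added.

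The cost is wording only: no change to subjects, visits or measurements. The sponsor gives up claiming efficacy from an unplanned analysis, though such analyses may still be run and shown. The sponsor also accepts the limited power of a yes/no endpoint at 30 per arm: for assumed success rates of 20% and 50% it is about 69%, and for 20% and 40% about 39%.

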10.1 Study endpoints

10.1.1 Primary endpoint

During treatment or after treatment OGTT 2 hours result is < 140 mg/dl, fasting blood sugar is < 100 mg/dl and HbA1c is < 6.0 % it will be treated as successful outcome of the treatment.

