5.1 Criteria for Exclusion:

Subjects with age below 30 and above 60 years are excluded in the study. The subjects are excluded in the study those who are known Diabetes, Malignant and accelerated hypertensive, Chronic Liver and Renal diseases, Coronary artery disease, Secondary Diabetes mellitus, CNS disorder (e.g. encephalopathy) and patient undergoing regular treatment for any other severe illness. Pregnant woman and planning to be pregnant within six months and lactating mother are excluded.

6. Study Drug:

The intervention group receives either trial drug or life style modification. The trial drug is an official Siddha formulation mentioned in Siddha Formulary. Recent animal studies have also proved its anti-diabetic activity. It is a kayakalpa drug having anti-oxidant potential, hypothetically assumed to act in IGT.

Dose: 500 mg Tablet , 4 tablets twice a day. Dose as per the market availability and the dose 4 gm / day is as per Marundhu Alavu Attavanai mentioned in Gunapadam Thatthu Jeeva Vaguppu.

The LSM group will be advised to adopt life style modifications (balanced diet along with brisk walking not less than 150 min/week.) These interventions will be measured via LSM intervention compliance form.

Duration of the medication: 180 days. Duration is to measure the range of HbA1c.

6.1 Study drug Compliance/Adherence:

The container will be checked and the tablets will be counted by which compliance will be checked during each and every visit. It can also be assessed based on the drug compliance

form (Form IV A) for drug intervention group. The LSM group can be assessed based on the LSM intervention compliance form (Form IV B).

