14. RBC _____ (HPF)
15. Cast _____ (HPF)

Stool examination

16. Routine _____

Microscopic

17. Ova _____ 18. Cyst _____ 19. Occult Blood _____

Blood

20. TC (Cells/Cumm) _____

Differential Count

21. P (%) _____ 22. L (%) _____ 23. E (%) _____ 24. M (%) _____ 25. B (%) _____

26. Hb (g/dl) _____.

27. ESR (1/2 hour.) _____ ESR (1 hour.) _____

28. Blood Sugar- Fasting (mg/dl) _____

29. Blood Sugar – OGTT (mg/dl) _____ (After 2 hours)/ PP _____ (mg/dl)

30. Glycated Hemoglobin (HbA1c) _____ (to be done before treatment and at the end of treatment)

31. Blood Urea (mg/dl) _____

32. S. Creatinine (mg/dl) _____

33. Uric acid (mg/dl) _____

LIPID PROFILE

34. Serum total Cholesterol (mg/dl) _____

35. S. Triglycerides (mg/dl) _____

36. HDL (mg/dl) _____

37. LDL (mg/dl) _____

38. VLDL (mg/dl) _____

LIVER FUNCTION TEST

Serum Bilirubin

39. Total (mg/dl) _____

40. Direct (mg/dl) _____

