41. SGOT (IU/L) _____

- 42. SGPT (IU/L) _____
- 43. Alk. Phosphatase (KA units) _____
- 44. Total proteins (gm/dl) _____
- 45. Albumin (gm/dl) _____
- 46. Globulin (gm/dl) _____
- 47. A/G Ratio _____

Serum Electrolytes

- 48. Sodium (mEq/L) _____
- 49. Potassium (mEq/L) _____
- 50. Chloride (mEq/L) _____

Sl.No.10-50 will be done during I visit (0 day), IV visit (90th day) and VII visit (180th day).

Sl.No.28 & 29 (Blood Sugar- F & PP) in the following visits II, III, V and VI.

Date:

--	--

--	--

--	--

Signature of Investigator/ Medical Officer

**OPEN LABELED RANDOMIZED CONTROLLED CLINICAL TRIAL ON
IMPAIRED GLUCOSE TOLERANCE –IGT (Munneerizhivu)**

**FORM II - CLINICAL & PHYSIOLOGICAL ASSESSMENT
[Before Treatment & During monthly visit]**

1 st visit – 0 day		5 th visit – 120 th day	
2 nd visit – 30 th day		6 th visit – 150 th day	
3 rd visit – 60 th day		7 th visit – 180 th day	
4 th visit – 90 th day		8 th visit – 210 th day	

1. Code No. (Clinical trial)
2. Centre : Siddha Central Research Institute, Arumbakkam, Chennai.
3. Name of the Patient _____
4. S. No. of Patient _____
5. Gender Male (1) Female (2)
6. Date of Birth Age (Years)
7. Address _____

Chief complaint with duration (if any) in days (mostly asymptomatic)

- | | Absent (0) | Present (1) |
|------------------------------------|---|---|
| 8. Polyuria (Excessive Urine) |  |  |
| If present, duration in days _____ | | |
| 9. Polyphagia (Excessive Hunger) |  |  |
| If present, duration in days _____ | | |
| 10. Polydipsia(Excessive Thirst) |  |  |

If present, duration in days _____

11. Exhaustion/Tiredness

If present, duration in days _____

Absent (0)

Present (1)

12. Body ache

If present, duration in days _____

VITAL SIGNS

13. Pulse rate/min

14. Heart rate/min

15. BP(mm of Hg)

 /

16. Temperature °F

 .

PRESENT(1)

ABSENT (2)

17. Cyanosis

18. Anaemia

19. Jaundice

20. Clubbing

21. Lymphadenopathy

22. Oedema

23. Height/cm

 .

24. Weight/Kgs

 .

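### The primary endpoint accepts success at any time during or after treatment, with no named visit and no requirement that its three components come from the same visit

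*Protocol*

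**What the plan says.** Section 10.1.1 defines success in one sentence. It begins "During treatment or after treatment OGTT 2 hours result is < 140 mg/dl" and ends "fasting blood sugar is < 100 mg/dl and HbA1c is < 6.0 % it will be treated as successful outcome of the treatment". The three limits are joined by 'and'. No visit is named, nothing says the three values must come from one visit, and there is no rule for a participant who qualifies and later relapses.

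Section 2.1 uses the same window: "If, during treatment or after treatment OGTT 2 hours remain between 126 mg/dl and 140 mg/dl". Its verb hints at persistence, but no period is attached to it.

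Section 11 describes treatment success as IGT not turning into overt diabetes and says this is measured by the primary endpoint. Section 6 links the treatment period to one component: "Duration of the medication: 180 days. Duration is to measure the range of HbA1c".

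The schedule at the end of Form III reads "Sl.No.10-50 will be done during I visit (0 day), IV visit (90th day) and VII visit (180th day", a range that includes fasting glucose (item 28), OGTT/PP (item 29) and HbA1c (item 30). For the other treatment visits it reads "Sl.No.28 & 29 (Blood Sugar- F & PP) in the following visits II, III, V and VI". Item 30 of the same form limits HbA1c differently: "to be done before treatment and at the end of treatment". Section 7.1 also places HbA1c only before and after treatment. Section 7.2 adds one month of observation after treatment stops (visit 8, day 210) and names physical assessment and OGTT there, but not HbA1c.

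**The concern.** This is not a detail left to a statistical analysis plan. The protocol does fix the timing of its primary endpoint, and the rule it fixes can give an answer that conflicts with the trial's own criterion of success. Section 11 is about staying free of diabetes. A rule that is satisfied once and never revisited can count someone who has become diabetic by the end of treatment.

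The rule also leaves the primary result not uniquely defined. The trial is open-label (section 3), the investigator analyses the data (section 12), and section 10 leaves further analysis to depend on the results. With no visit fixed, the visit or combination of visits that is scored could be settled after the values are known. Success also comes to depend on how many assessments a participant attended, and attendance may differ between arms when both sides know the allocation.

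**Working it through.** **The plan's own figure.** There is none to reproduce. The protocol states no expected success rate, and section 10.2 justifies 60 participants (30 per arm) by trial phase alone.

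**Step 1: how many complete occasions exist.**

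| Day | Glucose | HbA1c, Form III schedule | HbA1c, 7.1 and Form III item 30 |
|---|---|---|---|
| 0 | fasting, OGTT/PP | yes | yes |
| 30, 60 | fasting, PP | no | no |
| 90 | fasting, OGTT/PP | yes | no |
| 120, 150 | fasting, PP | no | no |
| 180 | fasting, OGTT/PP | yes | yes |
| 210 | OGTT (7.2) | not named | not named |

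Under the Form III schedule there are two post-baseline occasions with all three components. Under 7.1 and item 30 there is one, day 180. Even then, a day-180 HbA1c could be paired with normal glucose values from an earlier visit, because nothing in 10.1.1 excludes it.

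**Step 2: apply the rule to one pattern.** All three limits are met at day 90, and values are in the diabetic range at day 180. Section 10.1.1 read literally gives success. Section 11 gives failure, since IGT has become diabetes. The two sections disagree about the same participant.

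**Step 3: size of the difference.** Let *p* be the success rate at a single visit, taken as equal at days 90 and 180, and *b* the probability of success at both. Then

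- ever-met rate = 2*p* − *b*
- excess over the day-180 rate = *p* − *b*, the share who qualify at day 90 and not at day 180.

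This excess cannot be negative, so the direction needs no assumption. Its size does. I take *b* from a bivariate normal with latent correlation *r*: *b* = Φ₂(*c*, *c*; *r*), with *c* = Φ⁻¹(*p*). Both *p* and *r* are assumptions; neither is in the protocol.

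| *p* | *r* | *b* | 2*p* − *b* | Excess | Excess × 30 |
|---|---|---|---|---|---|
| 0.30 | 0.8 | 0.211 | 0.389 | 0.089 | 2.7 |
| 0.30 | 0.5 | 0.157 | 0.443 | 0.143 | 4.3 |
| 0.30 | 0 | 0.090 | 0.510 | 0.210 | 6.3 |
| 0.20 | 0.8 | 0.129 | 0.271 | 0.071 | 2.1 |
| 0.20 | 0.5 | 0.087 | 0.313 | 0.113 | 3.4 |
| 0.20 | 0 | 0.040 | 0.360 | 0.160 | 4.8 |

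The rows with *r* = 0 are a bound, not a realistic case for repeated measurements on one person.

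**Step 4: effect on the difference between arms.**

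- 20% v 30%, *r* = 0.8: 27.1% v 38.9%. The gap goes from 10 to 11.8 points.
- 20% v 40%, *r* = 0.7: 28.7% v 52.2%. The gap goes from 20 to 23.5 points.
- 50% v 70%, *r* = 0.7: 62.7% v 81.0%. The gap goes from 20 to 18.3 points.

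With independent visits the new gap is (1 − *p*₁)² − (1 − *p*₂)² = (*p*₂ − *p*₁)(2 − *p*₁ − *p*₂), which is smaller than *p*₂ − *p*₁ only when *p*₁ + *p*₂ > 1. The gap can therefore move either way.

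**The case against.** Three stronger readings are tempting, and the documents do not support them.

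- *Success can be scored at any of the seven or eight visits.* One of those visits is baseline, the four interim visits have no HbA1c, and none is named at day 210. At most two post-baseline visits carry the full composite, possibly only one. More chances than that arise only by combining components across visits, which the text neither allows nor forbids.
- *Best-of-visits scoring shrinks the treatment contrast.* Step 4 shows that it widens at low success rates and narrows at high ones.
- *The rule biases the comparison.* Both arms have the same rule and schedule, so higher rates in each are not in themselves a bias. Bias would need attendance, number of assessments or choice of visit to differ by arm. The design leaves room for that, but nothing in the protocol shows that it will happen, and with one or two complete occasions the scope for unequal attendance is small.

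There is also a fair argument that the protocol intends a sustained response: the verb in 2.1 suggests persistence, and section 11 speaks of non-progression. But 2.1 gives no period, the verb is absent from 10.1.1, and 2.1 carries the same open window. These passages add a conflict to be reconciled; they do not supply the missing visit.

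Last, the trial calls itself exploratory. That may soften how the result is used, but it does not remove the need for one definition of the primary outcome when a wording change provides it.

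**Conclusion.** The point holds. As worded, the primary endpoint can count as a success a participant who is diabetic at the end of treatment, contrary to section 11, and it does not determine which visit, or which combination of visits, is scored.

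That the ever-met rate is never below the day-180 rate is certain. The size is conditional on assumed rates and correlations, equal rates at both visits, and the Form III schedule with HbA1c at day 90. On those terms 30% becomes about 39-44%, with 51% as the bound, and 20% becomes about 27-31%, with 36% as the bound. At correlations of 0.5 to 0.8 that is roughly two to four extra successes in an arm of 30.

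If HbA1c is taken only before and at the end of treatment, these two-occasion figures do not apply, and the remaining problem is the pairing of components from different visits.

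**What to change.** - In 2.1 and 10.1.1, replace the open window with: *at the day-180 visit (visit VII), with all three components from that visit*.
- Reconcile HbA1c timing between 7.1, Form III item 30 and the schedule at the end of Form III.
- Report day 90 as supportive. It can be the full composite only if HbA1c is taken then; otherwise it covers glucose alone.
- Report the day-210 OGTT separately as durability after treatment stops. The composite is not available there, since 7.2 names no HbA1c.

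The cost is one phrase in two sections plus alignment of the HbA1c statements. The primary endpoint needs no new measurement, because day 180 carries all three components under either HbA1c reading. The downside is that reported success rates will be somewhat lower than under the open window.

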7.1 Screening procedures

The full details of history, physical examination, anthropometric measurements, 24-hours diet recall, physical activity of the patients will be recorded as per the proforma. OGTT is the critical investigation for this study and based on this the screening will be done. Investigations - HbA1c and Fasting blood sugar, Lipid profile, Liver function test, Renal function test, Electrolytes and Urine analysis will be taken before and after treatment and the reports will be recorded.

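### The primary endpoint turns three continuous glucose measures into one joint yes/no with 30 per arm; a baseline-adjusted comparison of values already collected would usually be more precise

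*Protocol*

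**What the plan says.** Section 10.1.1 of the protocol defines the primary endpoint as a joint condition, "OGTT 2 hours result is < 140 mg/dl, fasting blood sugar is < 100 mg/dl and HbA1c is < 6.0" per cent. When it is met, "it will be treated as successful outcome of the treatment". Each participant therefore contributes one success or one failure.

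The success cuts sit at the lower entry limits. Section 5 states that "2 hours OGTT should be between 140 mg and 199 mg", with fasting glucose above 100 mg/dl and HbA1c above 6.0%.

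Section 10.2 gives the size: "60 is the sample size as per the phase (Exploratory trial) of the clinical trial. 30 subjects will be enrolled in each group". It states no effect size, SD, success rate or power.

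Form III, items 28 to 30, records fasting glucose, 2-hour OGTT (or PP) and HbA1c as numbers. Its footnote schedules the whole panel on days 0, 90 and 180.

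Section 10 also plans means with SD, a comparison of means by ANOVA and paired t tests for differences between means. It names chi-square for association with risk factors. It does not say which test compares the arms on efficacy, and it mentions no adjustment for baseline.

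**The concern.** A joint yes/no ignores how far each marker moved. A participant who goes from an OGTT of 141 to 139 mg/dl meets that component. One who goes from 199 to 141 mg/dl, a fall of 58 mg/dl, fails it and is scored the same as someone who did not change. Missing one cut by 1 mg/dl cancels any improvement in the other two markers.

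In a 60-person exploratory trial the most useful product is a reasonably precise estimate of the drug effect. A difference between two proportions with 30 per arm is imprecise, and a real effect can easily be missed. The measurements needed for a sharper estimate are already planned. The issue is the scale of the endpoint, so it would remain if the cut-offs and the visit were settled and a test of proportions were named.

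**Working it through.** **Plan's own figure.** The 60 in Section 10.2 cannot be reproduced, because it rests on the trial phase and not on a calculation. What follows is an illustration.

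**Inputs.** From the protocol: 30 per arm, and a three-part success rule. Assumed: two-sided 5% (Section 10 gives 0.005 or 0.05, and only for correlation); no dropout; a drug shift of d = 0.74 SD; markers jointly normal with pairwise correlation 0.3, 0.5 or 0.7; 30% or 50% of controls below each cut; baseline correlation 0.5. The value 0.74 is the shift that 30 per arm detects with about 80% power on one continuous marker.

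**Step 1: one continuous marker.** The t-test noncentrality is d × √(n/2) = 0.74 × √15 = 2.87 on 58 degrees of freedom, giving power of 80.5%. ANCOVA raises the effective shift to 0.74/√(1 − 0.5²) = 0.854. The noncentrality is then 0.854 × √15 = 3.31, giving power of about 90%.

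**Step 2: the composite, equal shift on all three markers.** Success rates are trivariate normal probabilities of falling below all three cuts. Power is the uncorrected chi-square, by exact enumeration of 30 against 30.

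| Correlation | Controls below each cut | Success, control | Success, drug | Power |
|---|---|---|---|---|
| 0.3 | 30% | 6.6% | 28.0% | 62% |
| 0.3 | 50% | 19.8% | 52.1% | 76% |
| 0.5 | 30% | 10.1% | 33.4% | 61% |
| 0.5 | 50% | 25.0% | 56.7% | 72% |
| 0.7 | 30% | 14.4% | 39.6% | 61% |
| 0.7 | 50% | 31.0% | 61.8% | 69% |

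(The normal approximation gives 59% to 76%.)

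**Step 3: unequal shifts.** Over the same six settings, if one marker shifts 0.74 SD and the other two shift 0.37 SD, composite power is 27% to 38%. If only one marker shifts, it is 7% to 9%. A t test on the marker that shifts by 0.74 SD stays at about 80% in both cases.

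**Step 4: information loss.** For 80% power on one continuous marker, n = 2 × (1.96 + 0.84)²/0.74² = 28.7, so 29 per arm. With the equal shift of Step 2, the two-proportion formula, n = [1.96√(2p̄(1 − p̄)) + 0.84√(p₁(1 − p₁) + p₂(1 − p₂))]²/(p₂ − p₁)², gives 34 to 49 per arm. Relative efficiency is 29/49 = 0.59 to 29/34 = 0.85, a loss of about 15% to 41%.

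**Step 5: where the gain shrinks.** A simulation was run with assumed SDs of 28 mg/dl (OGTT), 10 mg/dl (fasting) and 0.3% (HbA1c), and an equal drug shift of 0.6 or 0.8 SD on every marker. It compared ANCOVA of OGTT with chi-square on the composite. The gain was 7 to 26 points when lifestyle modification alone shifted the markers by 0.2 SD, and 0 to 10 points when it shifted them by 0.5 SD.

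**Not modelled in Steps 1 to 4.** Success reached at any time during or after treatment, and participants who already meet one or two of the cuts at entry. Both would change the success rates.

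**The case against.** The strongest reply has four parts.

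- **The continuous values are not thrown away.** A reader might infer from Section 10.1.1 that they are. Section 10 does not support that, since it plans means, ANOVA and paired t tests. This stands. What remains is that none of these is tied to the efficacy question, and a within-arm paired t test does not compare the arms.
- **No stated figure is wrong.** A reader might infer that the trial fails its own power target. It has none: "60 is the sample size as per the phase (Exploratory trial) of the clinical trial". This stands too, and every power figure above rests on assumptions.
- **Normalisation on all three markers is a meaningful participant-level result.** This stands in part, and is why the criterion should still be reported. Section 11, however, says the endpoint measures non-transformation to diabetes. A participant who ends at an OGTT of 150 mg/dl is still within the entry range, yet counts as a failure.
- **OGTT alone leaves two markers out of the main analysis.** The statement that "OGTT is the critical investigation for this study and based on this the screening will be done" comes from the screening section, and Section 6 links the 180-day duration to HbA1c. This is fair. Fasting glucose and HbA1c should therefore be analysed in the same way beside it.

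Two stronger readings should be avoided. That most of the information is lost is not shown: against one continuous marker the loss is 15-41%, and it passes half only in part of the range when all three markers are combined. Nor should a gain of 25 to 43 points be claimed. That is the single-cut comparison of chi-square with ANCOVA, which is not this endpoint and mixes the cost of dichotomising with the benefit of baseline adjustment.

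**Conclusion.** The point holds as an inexpensive improvement to the plan; it does not correct a wrong figure. With 30 per arm, two-sided 5% and an equal 0.74 SD shift, the composite has about 61-76% power, against about 80% for one continuous marker and about 90% with baseline adjustment. The equal shift favours the composite, which does much worse when the markers respond unequally. At the other end, if lifestyle modification alone has a strong effect and all markers move together, the gain may be close to zero. The direction is well supported, but the exact size cannot be derived from the protocol.

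**What to change.** In Sections 10.1.1 and 10:

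- Make the main between-arm efficacy analysis an ANCOVA of the day-180 2-hour OGTT in mg/dl, with arm as factor and the day-0 value as covariate. Report the adjusted mean difference with its 95% CI.
- Analyse day-180 fasting glucose and HbA1c in the same way, in place of unadjusted ANOVA and within-arm paired t tests.
- Keep the three-part normalisation criterion as a responder outcome, reported as a risk difference with 95% CI.
- On Form III, state that item 29 is the 2-hour OGTT value on days 0 and 180. It now offers OGTT or PP, and the footnote labels items 28 and 29 as fasting and PP, so the proposed outcome is not yet securely defined on the form.

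The cost is protocol and form wording. If item 29 is completed as the OGTT value, no extra visits, tests or participants are needed. The headline becomes a mean difference in mg/dl, which answers a different question from a success rate, so both should be reported.
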